6.3.4 Safety

Safety of the Tasso+™ device, as part of user experience, will be evaluated as the percentages of eligible participants who: (i) experience solicited local AEs including pain, tenderness, redness, swelling, or bruising within 7 days of Tasso+™ administration; (ii) experience unsolicited AEs within 28 days of Tasso+™ administration; (iii) experience a related Grade 3 AE, a related Grade 4 AE, a related AE leading to study discontinuation, or a related SAE within 28 days of Tasso+™ administration. This endpoint will be assessed throughout the conduct of the study.

Severity and causality definitions are provided in [Section 8.2](#).

6.3.5 Tolerability

Tolerability of the Tasso+™ device, as part of user experience, will be evaluated as the percentage of eligible participants who complete last Tasso+™ administration (Day 57).

6.3.6 Usability

Usability of the Tasso+™ device, as part of user experience, will be assessed using a Tasso questionnaire filled in the eDiary by participants immediately following each

Tasso+™ administration (on Days 1, 29, and 57) and on Day 85. The questionnaire includes questions about user experience, by assessing willingness to use Tasso+™ device again, the pain and discomfort experienced, the preference, the understanding of instructions, and the healing of the collection site hit.

6.3.7 *SARS-CoV-2 Infection Surveillance*

SARS-CoV-2 infection surveillance will be performed by assessing the percentages of eligible participants with: (i) a positive nasopharyngeal swab for SARS-CoV-2 PCR on Day 1 and (ii) seroconverting to SARS-CoV-2 between Days 1 and 57.

6.4 Safety Assessments

6.4.1 *Adverse Events*

AEs will be followed, recorded, and reported in line with the procedures described in [Section 8](#).

6.4.2 *Pregnancy*

Urine pregnancy tests will be performed for participants of childbearing potential on Day 1 as per Schedule of Assessment ([Table 1](#)). Regardless of the test result (positive or negative), the participant will remain eligible for study participation. The Investigator will record pregnancy information on the appropriate form and submit it to the Principal Investigator (PI) within 24 hours of the Day 1 Visit. Medical costs associated with the pregnancy follow-up will not be covered by the Sponsor, as the risk to participants has been considered non-significant (see [Appendix II](#)).

6.4.2.1 *Pregnant Trial Participant (Incidental Pregnancy)*

If a participant becomes pregnant, the participant will not be discontinued from the study. The Investigator will record pregnancy information on the appropriate form and submit it to the PI within 24 hours of learning of the participant's pregnancy. Medical costs associated with the pregnancy follow-up will not be covered by the Sponsor, as the risk to participants has been considered non-significant (see [Appendix II](#)).

6.4.2.2 *Pregnant Partner of a Trial Participant*

In the event that the female partner of a male participant becomes pregnant, inclusion of the female partner into the study for safety assessment is not relevant for this Class II medical device, as the risk to participants has been considered non-significant (see [Appendix II](#)). Medical costs associated with the pregnancy will not be covered by the Sponsor.

6.4.3 *Breastfeeding*

Safety assessment of breastfed children is not relevant for this Class II medical device as the risk to participants has been considered non-significant (see [Appendix II](#)).

6.5 Sample Collection Storage

The remnants of biological samples from clinical trial participants will be stored by the Central Laboratory, for the duration of the study, in case any retesting is required. After completion of all protocol-specified testing (ie, after database lock), Central Laboratory will not maintain the biological samples any further.

7 INTERVENTIONS

7.1 Investigational Medical Device

Tasso kits which contain Investigational Medical Device will be shipped to the Sites by Central Laboratory in ICON kit boxes labeled “Exclusively for clinical trial”; no components in ICON kit boxes are investigational.

7.1.1 *Description of Investigational Medical Device*

Tasso+™ device is a sterile, disposable, integrated capillary blood collection device, including a lancet assembly and a detachable capillary collection tube for the collection of blood by a user or caregiver in remote settings. The device is designed to collect within 5 minutes up to 600 µL capillary blood. The Tasso+™ device is comprised of the collection unit (called Tasso Button) and a capillary collection tube that can be supplied in several different configurations allowing the transportation of the blood. The Tasso+™ device lancet is classified as an FDA 510(k)-cleared Class II medical device in the US. The Tasso+™ device is designed to safely and reliably collect blood in clinical settings, without the need of a highly trained phlebotomist, while minimizing pain to the participant. Total volume of capillary blood collected by Tasso+™ per application will not exceed 1 mL. Participants will have a Tasso+™ device with Tasso+™ kits which either include SST or EDTA capillary collection tube, to be placed on each upper arm at each visit. Shaving of the upper arm area to remove excess body hair may be required.

7.1.2 *Preparation, Handling, and Storage*

The Investigator (or designee) is responsible for the safe and proper storage of the medical device at the site. The medical device will be stored under controlled conditions according to the storage requirements described on the label(s), ie, 18 to 28°C (64.4 to 82.4°F). Tasso+™ kits will be stored under controlled conditions according to the storage requirements described on the label(s), ie, 18 to 25°C (64.4 to 77°F). The shelf lives of the Tasso+™ devices and Tasso+™ kits are of 12 months. The Investigator (or designee) will instruct the participants to store the medical device and kits in accordance with the instructions on the label(s).

7.1.3 *Sterilization*

The Tasso+™ kits are sterile. The Tasso+™ device is rendered sterile by e-beam irradiation in accordance with ISO 11137-1, 11137-2, 11737-1, and 11737-2 Sterilization of Healthcare Products. The Tasso+™ device was validated for a minimum sterility assurance level of 10⁻⁶ following VDmax25 kGy test methods after being built per processes intended for the final configuration of the device. The Tasso+™ device sterilization process is controlled through internal work instructions and checklists.

7.1.4 Packaging, Labelling, and Shipment

The medical device will be packaged and labelled in accordance with all applicable regulatory requirements and Good Manufacturing Practice guidelines.

The Tasso+™ is provided sterile and is packaged in an industry standard polymer tray and Tyvek cover as a primary sterile barrier. All system components are packaged in appropriately constrained packaging including corrugated boxes and labelling.

Shipping is performed in accordance with Tasso SOP for the control and handling of product. Records are kept providing lot traceability for each site and each product.

7.2 Blinding

This is an open-label study. Participants, HCPs, and laboratory technicians will not be blinded to the study intervention.

7.3 Method of Assigning Process

Each participant will have a unique subject screening number obtained from the interactive voice response system (IVRS). Once the participant is deemed eligible, the participant will be assigned a randomization number.

Randomization will be performed via a centralized IVRS. On Day 1, eligible participants will be assigned to either Cohort A or Cohort B in a 2:1 ratio. Each participant will receive a unique randomization number when he/she is assigned treatment. Participants will be allocated to treatment according to the randomization code.

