4.2 Steps to the Process

4.2.1 *Training*

Training will be provided on Days 1 and 29 and will include detailed IFU and online video training. The detailed IFU will be provided in a separate document, and an overview of IFU is provided in [Section 7.4](#). When administering the Tasso+™ remotely, participants will receive proctor-support from the Site on Day 29 (and as requested, on Day 57) during working hours, the intent being to guide the participant through the process and to help troubleshoot should any difficulties be encountered. Training on Day 57 should be performed only if it is specifically requested due to participant hesitation.

4.2.2 *Blood Collection*

Once trained, and by following the IFU provided (see [Section 7.4](#)), participants will self-administer the Tasso+™ device in the Clinic at the Investigator site (supervised) and subsequently remotely, ie, at home or a suitable remote location (proctor-supported on Day 29 and unsupported on Day 57). Self-collection may be additionally supported on Day 57 using a proctor session, as requested, to guide the participant through the process and help to troubleshoot any difficulties. The SST tube will be preferably collected from the left upper arm and the EDTA tube will be preferably collected from the right upper arm.

As per IFU, participants will have to gently invert the Tasso+™ capillary collection tubes after the full collection process is completed.

4.2.3 *Blood Volume and Clotting Analyses*

Blood volume and clotting analyses will be assessed before centrifugation. Thus, for Cohort B, on Day 1, these endpoints will be assessed by the Site, while for Cohort A, on Day 1 and for Cohorts A and B combined on Days 29 and 57, these endpoints will be assessed by the Central Laboratory (see [Section 6.3](#)).

4.2.4 *Centrifugation*

Tasso+™ blood samples of participants randomized to Cohort A, collected on Day 1, will be centrifuged upon receipt by the Central Laboratory, as per the real-world use of Tasso+™.

Tasso+™ blood samples of participants randomized to Cohort B, collected on Day 1, will be centrifuged and aliquoted by the Site before shipping, following the same procedure as for venipuncture blood samples.

Tasso+™ blood samples of participants from both Cohorts A and B, collected on Days 29 and 57, will be centrifuged upon receipt by the Central Laboratory, as per the real-world use of Tasso+™.

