6.2 Study Visits (Days 1, 29, 57, and 85)

The Day 1 Visit will occur at the clinical site and subsequent visits on Study Days 29, 57, and 85 will occur remotely. On Day 1, participants will be provided and trained on an eDiary that will allow them to record their symptoms (Symptom questionnaire) and usability (Tasso user questionnaire). The eDiary entries will be reviewed at each visit and any recorded symptoms will be entered into the electronic data capture (EDC) database.

Participants will complete the user questionnaire (available in eDiary), provided by Tasso, immediately following each Tasso+™ device administration. The user questionnaire consists of questions about their user experience including assessing their willingness to use the Tasso+™ device repeatedly and at what frequency, any pain or discomfort experienced, their preference to venipuncture and finger-sticks, the ease of comprehension of the instructions and training, and the healing of the collection site.

Venous blood will be obtained from participants at the clinical site on Day 1 using syringe or Vacutainers, as described in the Schedule of Assessments ([Table 1](#)). Heart rate and blood pressure measurements should be taken in the supine position, preceded by at least 5 minutes of rest. Body temperature will be taken by ear/tympanic/temporal, oral, or forehead method.

Clinician supervised collection of blood using the Tasso+™ device will be performed at Day 1 Visit and collection of blood using the Tasso+™ device will be performed remotely on Day 29 (proctor-supported) and on Day 57 (intended to be unsupported). There will be two collections, one from each arm; left upper arm will be preferably used for serum preparation (Tasso+™/SST capillary collection tube with gold cap, see [Table 2](#)) and right upper arm will be preferably used to collect whole blood (Tasso+™/EDTA capillary collection tube with lavender cap, see [Table 2](#)). During Visits 2 and 3 (Days 29 and 57), Tasso+™ device will be self-administered by the participant. On Day 29, the self-collection will be supported by a proctor (during working hours). On Day 57, self-collection may be additionally supported by a proctor to guide the participant through the process and help to troubleshoot any difficulties (during working hours). Contact information will be provided to each participant in the event they have concerns or they need help while using Tasso+™ device.

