6.2 Randomization

Each participant will have a unique subject screening number obtained from the interactive voice response system (IVRS). Once the participant is deemed eligible, the participant will be assigned a randomization number.

Randomization will be performed via a centralized IVRS. On Day 1, eligible participants will be assigned to either Cohort A or Cohort B in a 2:1 ratio. Thus, it is planned to randomize approximately 133 participants into Cohort A and approximately 67 participants into Cohort B.

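### Cohort is assigned openly at eligibility and nothing withholds it until the Day 1 tubes are capped, so staff could know it during collection and blur the descriptive A versus B contrast

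*Protocol*

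**What the plan says.** **Assignment.** Protocol 7.3 and SAP 6.2 tie the randomization number to eligibility: "Once the participant is deemed eligible, the participant will be assigned a randomization number". SAP 6.2 adds: "On Day 1, eligible participants will be assigned to either Cohort A or Cohort B in a 2:1 ratio". Table 1 of both documents lists IVRS randomization directly under the eligibility check and above the Tasso+ collection rows.

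**Masking.** There is none. Protocol 7.2 states: "Participants, HCPs, and laboratory technicians will not be blinded to the study intervention".

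**What cohort changes.** Under Protocol 4.2.4, Cohort A tubes "collected on Day 1, will be centrifuged upon receipt by the Central Laboratory, as per the real-world use of Tasso+™", and Cohort B tubes "collected on Day 1, will be centrifuged and aliquoted by the Site before shipping, following the same procedure as for venipuncture blood samples". Protocol 4.2.3 also splits the reading of volume and clotting, which precedes centrifugation: "for Cohort B, on Day 1, these endpoints will be assessed by the Site". For Cohort A the Central Laboratory reads them. Training, instructions, device, kits and supervision are the same in both cohorts.

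**Day 1 collection.** Participants collect their own samples, but not alone. Protocol 6.2 states: "Clinician supervised collection of blood using the Tasso+™ device will be performed at Day 1 Visit".

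**Use of the contrast.** Protocol 1.2 says that the effect of centrifugation timing on sample integrity and accuracy will be evaluated on Day 1 by means of the two cohorts. Four of the five primary endpoints in Protocol 3.1 (two on integrity, two on correlation) are reported by cohort on Day 1.

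**The concern.** Cohort is the only randomised feature of the study. The A versus B comparison isolates centrifugation timing only if collection is alike in both cohorts. If supervising staff know the cohort, the help they give, the time they allow, their attention to tube inversion and their readiness to arrange another attempt could differ by cohort. For Cohort B the Site will itself read and spin the tube; for Cohort A it ships the tube unspun.

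A second route is through the denominator. Sample integrity is a percentage of samples collected. A tube that is never obtained after assignment can drop out of that percentage. If such losses differed by cohort, the samples compared would no longer be those that randomisation balanced.

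No conduct reason is given for knowing the cohort before the tubes are capped, so the exposure is avoidable.

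**Working it through.** **1. Order of events.**
- Assignment on Day 1 follows eligibility (Protocol 7.3, SAP 6.2), and the row order of Table 1 is consistent with assignment before collection.
- Neither document states whether the IVRS call comes before or after the Tasso+ collection.
- Everything that depends on cohort (reading volume and clotting, centrifuging, aliquoting) comes after collection (Protocol 4.2.3 and 4.2.4).
- Neither document withholds the cohort from collection staff.

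It follows that knowledge of cohort during collection is permitted and is not needed. That it occurs is an inference.

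**2. Cohort sizes.** About 200 participants at 2:1 give 200 × 2/3 = 133.3 and 200 × 1/3 = 66.7. This matches the stated 133 and 67 (Protocol 9.3, SAP 6.2). The plan has no power calculation to reproduce.

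**3. Random error of the Day 1 difference between cohorts.** SE = sqrt[p(1 − p)(1/133 + 1/67)], and the 95% half-width is 1.96 × SE. The plan gives no planning rate, so p is an assumption. The range runs from the 70.0% to the 94.5% that Protocol 1.2 quotes from two earlier studies.

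| Assumed rate p | SE (points) | 95% half-width (points) |
|---|---|---|
| 70.0% | 6.9 | 13.5 |
| 80% | 6.0 | 11.7 |
| 94.5% | 3.4 | 6.7 |

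At 80%: sqrt(0.8 × 0.2 × (1/133 + 1/67)) = 0.060.

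**4. Failed collections that could fall after assignment.** Day 1 is supervised, so the relevant figure in Protocol 1.2 is the 94.5% supervised success rate, or 5.5% failure. Then 0.055 × 133 = 7.3 and 0.055 × 67 = 3.7: about 7 and 4 participants. This counts failed collections; it is not a bias.

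**5. Size of bias.** The documents give nothing from which to estimate it. As an illustration only, suppose that extra attention in one cohort rescued a share s of samples that would otherwise be inadequate. The spurious difference is then s × (1 − p).
- At p = 70.0%, s = 10% to 50% gives 3.0 to 15.0 points.
- At p = 94.5%, the same shares give 0.55 to 2.75 points.

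The values of s are invented to show the range. Zero is equally compatible with the documents.

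**The case against.** The strongest case against acting is that the bias is hypothetical.
- Participants collect their own samples after the same training. The instructions for use (Protocol 7.4) end collection at a set time or when the tube is full.
- The hemolytic index, chemistry and serology are measured by the Central Laboratory.
- Testing accuracy is a within-participant correlation of capillary and venous samples, computed separately in each cohort.
- There is no between-cohort test (SAP 9.5.1), so no type I error is at risk.

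All of this stands. It confines the harm to interpretation, mainly of the Day 1 integrity percentages.

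Three stronger readings are tempting, and the documents do not support them.
- **That staff do know the cohort at collection and that results are biased.** The order is inferred from Protocol 7.3 and Table 1, and neither a direction nor a size of bias is shown.
- **That up to 30% of participants (about 40 of 133 and 20 of 67) would be lost after assignment.** The 30% in Protocol 1.2 is participants without an adequate sample. Inadequate volume is a failure on the integrity endpoint, and a tube received with low volume stays in the denominator. The 6.6% failure rate in the same section comes from unsupervised use and does not describe Day 1. Losses also bias a comparison only if they differ by cohort.
- **That second kits are an established Day 1 route.** Protocol 4.3 words the repeat attempt for proctor-supported or unsupported collection. Protocol 6.3.3 allows an unscheduled kit without that limit, and both defer to a laboratory manual that is not among these documents. Whether the rule covers supervised Day 1 collection is unclear.

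It is also true that later assignment leaves the firmer cohort difference untouched: volume and clotting are read by the Site for Cohort B and by the Central Laboratory for Cohort A.

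**Conclusion.** The point holds as an avoidable weakness in the timing of assignment. Cohort is open, is assigned on eligibility, and may be known while staff supervise a collection that it should not affect. The Day 1 contrast is the study's only randomised comparison, and Protocol 1.2 gives it a stated purpose, so it merits this protection even though the analysis is descriptive.

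No size of bias can be stated. The scale figures (SE 6.0 points and half-width about 11.7 at an assumed 80% rate; about 7 and 4 failed collections at 5.5%) show only the precision of the contrast and how many collections might fail after assignment. They rest on the planned 133 and 67, on an assumed rate, and on one cited study's supervised success rate carrying over. This is a cheap improvement. It does not invalidate the Day 1 results.

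**What to change.** In Protocol 7.3 and SAP 6.2, state that the IVRS releases the cohort only after both Day 1 Tasso+ collections (including any repeat kit, if used) and the venous draw are finished and the tubes capped, and before any centrifugation. Record the time of assignment and the time at which collection ended.

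Day 1 collection appears to be well advanced: SAP 9.5.2.1 describes the Cohort B Day 1 records in the past tense, and SAP 9.5.4.2 refers to collection instructions updated in December 2024. For participants already enrolled, compare the IVRS assignment time, where the system holds one, with the collection time that the instructions for use ask to be recorded. Report how many were assigned first, and state the limitation in the study report.

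The cost is a short wording change and an IVRS call made later in the same visit. The call must be prompt so that Site centrifugation is not delayed. The Site versus Central Laboratory difference in assessing volume and clotting needs its own remedy, or at least its own caveat.

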7.4 Instruction for Use

The section below provides an overview of the IFU. The detailed IFU will be provided in a separate document. Instructional video is available on Tasso Inc. website (<http://www.tassoinc.com/tassoplus-video>). The use of Tasso+™ kit is not intended for use in diagnostic procedures.

The Tasso+™ kit includes the sterile, disposable Tasso+™ blood lancing device, and the supplies necessary to administer the device.

When collecting a sample, the device will be held onto the skin by a mild adhesive. With a press of the button, a sterile lancet will puncture the skin, simultaneously creating a slight vacuum that will help capillary blood flow under gravity into a compatible tube. After a predefined time period, or when the tube is full, the device will be peeled off the skin. The tube will be removed and capped for shipment. The lancet is single use and automatically retracts into the device in a safe position after use.

Preparation steps notably include set-up of the participant, identification of the collection sites, insertion of applicable tube (SST or EDTA) into the device, and warming and cleaning of the collection site.

Collection step notably includes sticking of the device to collection site, activation of the lancet, filling of the tube, removal of the device, closure of the tubes, and inversion of the tubes.

Shipping and final steps notably include writing of participant's ID number on tube, placing of tube in return bag, recording of the time and date of collection, packaging and shipping of tubes to the Central Laboratory, and discarding of leftover material (excepting Tasso+™).

7.5 Precautions and/or Lifestyle Considerations

There are no lifestyle considerations (such as dietary or physical activity restrictions) for this study beyond those listed in the inclusion/exclusion criteria ([Section 5](#)). The Tasso+™ devices require a hair-free surface which may need the upper arm area to be shaved.

Tasso+™ device and kits are not intended for more than one use. They should not be used on more than one participant. Improper use of blood lancets can increase the risk of inadvertent transmission of bloodborne pathogens, particularly in settings where multiple participants are being tested.

For this Study, precautions for use are as follow:

- For use only on a single participant. Discard the entire device after use.
- Do not use after expiration date.
- Single use only.
- Keep out of reach of children.
- Minor bruising or residual marks may occur at the sample collection site.
- Do not resterilize.
- For external use only.
- Use while seated as fainting may occur with any blood sampling procedure.
- Refer to manufacturer's instructions for individual components.
- Do not use if tray has been opened or damaged.

